STATISTICAL ANALYSES PLAN

A replicated crossover study to explore individual variability of appetite responses to a standardised meal and any moderating influence of the FTO gene

Version 1

Investigators

[name]
[name]
[name] [name]

Address

School of Sport, Exercise and Health Sciences
Loughborough University
Leicestershire
[name]
United Kingdom

Correspondence

[name]: [name], [contact]

Statistical analyses plan

Between-genotype differences in participant characteristics will be quantified using linear mixed models with group (AA versus TT) modelled as a fixed factor. The presence of interindividual differences in blood marker and perceived appetite responses to a standardised meal will be examined according to three analytical approaches (Atkinson and Batterham, 2015; Senn et al., 2011; Senn, 2016). The three approaches, detailed recently by [name] et al. (2018), will be as follows:

- (i) The association between the first and second replicate of control-adjusted treatment effect will be quantified for each outcome using Pearson's correlation coefficients (Senn, 2016). The first meal condition in any participant's sequence will be paired to the first control condition in the same individual's sequence. Thresholds of 0.1, 0.3 and 0.5 will be used to label correlation coefficients as small, moderate and large, respectively (Cohen, 1988). This correlation coefficient quantifies the consistency of meal effect across the replicated experimental conditions.
- (ii) The following equation (Atkinson and Batterham, 2015) will be used to provide an overall estimate of the true (control condition adjusted) between-subject differences in treatment response:

$$SD_{IR} = \sqrt{SD_M^2 - SD_C^2}$$

SD_{IR} represents the true interindividual variation in treatment effect. SD_M and SD_C are the standard deviations of the pre-to-post change scores for the meal and fasted control conditions (averaged over the two replicates using the relevant equation for pooling SDs (Higgins and Green, 2011)).

- (iii) While the equation in (ii) estimates response variance adjusted for control condition change variance, the associated standard errors and confidence intervals (CI) are not appropriate for our within-subjects crossover study design, hence our adjunct approach of within-subjects general linear modelling. Using the MIXED procedure in SAS OnDemand for Academics (https://www.sas.com/en_us/software/on-demand-for-academics.html), a within-participant linear mixed model will be formulated to quantify any participant-by-condition interaction for each outcome. Condition and period (sequence), and their interaction effects,

will be modelled as fixed effects, and participant and participant-by-condition terms will be modelled as random effects. Standard residual diagnostics will be undertaken to assess the “influence diagnostics” of a potential set of observations on the adequacy and the stability of the modelled covariance parameter estimates (Oman, 1995; Schabenberger, 2004; West and Galecki, 2011).

The grand mean differences between conditions, and associated confidence intervals will be quantified with a within-subjects linear mixed model run in version 23 of SPSS (IBM Corporation, New York, USA) without the participant-by-condition random effect, but with a covariate of baseline values. The FTO genotype will be included in this model as a fixed between-subjects effect, and the genotype-by-condition interaction will be quantified.

Absolute standardised effect sizes (ES) will be calculated, with a standardised ES of 0.2 denoting the minimum important mean difference for all outcomes, 0.5 moderate and 0.8 large (Cohen, 1988). To calculate the minimal clinically important difference (MCID) for individual responses, the threshold of 0.2 for interpreting standardised mean changes (Cohen, 1988) will be halved, i.e. 0.1, and multiplied by the baseline between-subject SD (Atkinson and Batterham, 2015; Williamson et al., 2018). Pearson’s correlation coefficients will be quantified between the mean control-adjusted meal response for each of the appetite measures and body adiposity measurements. Pearson’s correlation coefficients will also be quantified between the pooled mean pre-to-post change in concentrations of plasma constituents and the pooled mean pre-to-post change in appetite perceptions across the four conditions.

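### Blood-marker individual response is assessed on pre-to-post change alone, so a response that is the same percentage in everyone can pass for true interindividual variation

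*SAP*

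**What the plan says.** The SAP sets out to examine "The presence of interindividual differences in blood marker and perceived appetite responses to a standardised meal" by three approaches.

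- **Approach (i)** correlates the control-adjusted meal effect between the two replicates.
- **Approach (ii)** takes SD_IR as the square root of SD_M² − SD_C². The two SDs are "the standard deviations of the pre-to-post change scores for the meal and fasted control conditions", and the SAP says that SD_IR "represents the true interindividual variation in treatment effect".
- **Approach (iii)** is a mixed model in which "participant and participant-by-condition terms will be modelled as random effects".

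For the MCID for individual responses, the 0.2 threshold "will be halved, i.e. 0.1, and multiplied by the baseline between-subject SD".

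No log, ratio or percentage scale is stated for any outcome. The later correlation analysis also works with "the pooled mean pre-to-post change in concentrations of plasma constituents". Baseline enters only the model for mean differences, which is fitted "without the participant-by-condition random effect, but with a covariate of baseline values". The model checks named are residual and influence diagnostics, with no rule for changing scale.

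**The concern.** A change score in concentration units is an absolute response. If the meal moves every participant's concentration by the same fraction, those with high baselines show large changes and those with low baselines show small ones, although nobody differs in proportional response. Baseline level is a stable feature of a person, so this pattern recurs in both replicates. Replication, which is meant to separate real individual response from noise, cannot remove it.

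The MCID is a multiple of the same baseline SD, so the comparison of SD_IR with the MCID can reduce to whether the common percentage change is above 10%. Individual variability is the title question of the study. A positive answer for a blood marker could then mean only that people start from different levels.

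**Working it through.** **Inputs.** From the SAP: the change-score definition, the SD_IR formula, the MCID of 0.1 × baseline SD, the terms of approach (iii), and P < 0.050. The SAP states no sample size, response size, baseline SD or assay error, so there is no figure of its own to reproduce. Assumed for illustration: n = 30, baseline mean 1 and between-subject CV 40% (s_B = 0.4), and within-subject CV 5%, 10% or 20% on pre and post values. An ANOVA F test stands in for approach (iii). Every participant has the same fractional change: p after the meal and c in the control.

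**Step 1. Approach (ii), equal noise v in both conditions.**

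SD_M² = p²s_B² + v and SD_C² = c²s_B² + v, so SD_IR = s_B × √(p² − c²). With c = 0, SD_IR/MCID = |p|/0.1, and the baseline SD cancels.

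| Common change, size | 5% | 10% | 20% | 30% | 50% | 100% |
|---|---|---|---|---|---|---|
| SD_IR/MCID | 0.5 | 1.0 | 2.0 | 3.0 | 5.0 | 10.0 |

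**Step 2. Approach (i), same conditions.** The control-adjusted effect is (p − c) × baseline plus noise from four measurements, each with SD e. The expected replicate correlation is about (p − c)²s_B² / [(p − c)²s_B² + 4e²]. For a 30% fall and flat control, the numerator is 0.09 × 0.16 = 0.0144.

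- e = 0.05: 0.0144/0.0244 = 0.59
- e = 0.10: 0.0144/0.0544 = 0.26
- e = 0.20: 0.0144/0.1744 = 0.08

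Simulation (1,000 runs each) gave median r of 0.58, 0.27 and 0.07. The participant-by-condition test was significant in 98%, 49% and 11% of runs, and SD_IR was above the MCID in 100%, 95% and 67%.

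**Step 3. Noise proportional to the level.** Post-meal noise now scales with (1 + p), so SD_M² − SD_C² = p²s_B² + [(1 + p)² − 1] × CV² × (1 + s_B²). For a 30% fall at CV 20%: 0.0144 − 0.51 × 0.04 × 1.16 = 0.0144 − 0.0237 = −0.0093, and SD_IR is undefined. For a 50% rise at CV 10%: 0.0400 + 1.25 × 0.01 × 1.16 = 0.0545, larger than under equal noise. Simulated, with a flat control:

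| Common change | CV | Median SD_IR/MCID | Above MCID | Median r | Interaction significant |
|---|---|---|---|---|---|
| 30% fall | 5% | 2.8 | 100% | 0.60 | 98% |
| 30% fall | 10% | 2.2 | 76% | 0.26 | 47% |
| 30% fall | 20% | negative difference | 34% | 0.08 | 18% |
| 50% rise | 10% | 5.6 | 100% | 0.41 | 75% |
| 50% rise | 20% | 6.9 | 97% | 0.14 | 26% |

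The 34% shows no excess. With equal noise at CV 20%, a mere 5% response put SD_IR above the MCID in 45% to 48% of runs, through imprecision alone.

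**Step 4. A fasted control that changes.** For a 30% fall after the meal, √(p² − c²)/0.1 is 2.83 when the control moves 10% in either direction, 2.24 at 20% and 0 at 30%. Approaches (i) and (iii) depend on (p − c)² instead. With −30% after the meal and +30% in control, that is 0.36, against 0.09 with a flat control. A simulation of this case gave r = 0.73 and a significant result in essentially every trial, while SD_IR is zero by the algebra.

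**Step 5. Where the error enters.** Take a 30% fall, baseline CV 50% and visit-to-visit CV 15%. The interaction test was significant in 91% and 38% of trials (residual CV 10% and 20%) when residual error was placed on the post value only, and in 60% and 21% when it was on both pre and post. In these runs at residual CV 20%, SD_IR exceeded the MCID in only 34–44% of trials.

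**Step 6. Log scale.** Here log(post/pre) = log(1 + p) plus error, and baseline drops out. With proportional noise, the simulations in step 3 gave SD_M² − SD_C² of about 0, median r between −0.02 and 0.01, and a significant interaction in about 3–6% of runs.

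**The case against.** A reader might infer that any common percentage change above 10% would automatically be reported as true and clinically important. The document does not support that. Steps 3 to 5 show that approach (ii) can miss the effect or go negative, and that detection by (i) and (iii) depends strongly on noise. The SAP also defines the MCID without stating a rule that declares importance when an SD_IR estimate exceeds it.

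A second objection is that proportional response is an assumption. The SAP lists no markers and gives no response sizes or assay errors, so it neither supports nor excludes it. This stands, and it limits the point to what could happen.

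A third is that absolute change is a legitimate estimand, and variation on that scale is real on that scale. The log scale is not neutral either. When everyone was given the same absolute rise, the log-scale interaction test rejected in 18–97% of simulated trials, depending on the rise and the error model, against 9–11% on the raw scale. This also stands. It rules out calling the raw analysis wrong, and it rules out making persistence on the log scale the sole gate for a claim.

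What survives is that the plan calls the result true variation without saying on what scale, and has no check that separates differing response from differing baseline. The influence diagnostics do not supply one, and the baseline covariate is in a model that does not estimate individual response. The disagreement between approaches in steps 3 and 4 is a further sign that the scale needs fixing in advance.

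**Conclusion.** The point holds in conditional form. For a blood marker that responds roughly in proportion to its level, with a stable fasted control and similar noise in both conditions, a uniform percentage response yields SD_IR of about |p| × baseline SD and passes the MCID once |p| exceeds 10%. Replication does not protect against it: for a common 30% fall, the interaction test was significant in 11% to 98% of simulated runs with equal noise, against a nominal 5%.

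These rates rest on the assumed n = 30, CVs and error models, and on an F test in place of the planned mixed model. That change scores apply to (i) and (iii) is inferred from the absence of any other stated scale. How far any actual marker is affected cannot be settled from the SAP. The matter is worth correcting because it bears on what the trial may conclude about its main question.

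**What to change.** For plasma concentrations, prespecify a sensitivity analysis that repeats (i)–(iii) on log(post/pre), with the MCID defined on the same scale as 0.1 × the SD of log baseline. Report both scales. Where individual differences appear on only one, describe them as scale-dependent and possibly explained by baseline level, not as true individual response. Keep raw scores for the appetite ratings.

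The cost is a few sentences in the SAP and one repeat of the same models per blood marker; trial conduct does not change. The downside is two sets of results for each marker, with the log-scale results read as ratios.

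### SD_IR in approach (ii) is built from pooled single-visit SDs; averaging each participant's two visits first would be more precise and would halve, not remove, any bias from unequal visit noise

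*SAP*

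**What the plan says.** The SAP (section Statistical analyses plan, approach (ii)) sets SD_IR equal to the square root of SD_M² − SD_C². The formula "will be used to provide an overall estimate of the true (control condition adjusted) between-subject differences in treatment response", and the SAP adds that "SD_{IR} represents the true interindividual variation in treatment effect".

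On the ingredients it says "SD_M and SD_C are the standard deviations of the pre-to-post change scores for the meal and fasted control conditions", and that these are "averaged over the two replicates using the relevant equation for pooling SDs". So an SD is taken across participants at each replicate, and the two SDs are then pooled. A participant's two visits are not averaged first.

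The SAP does not state that visit-to-visit variance is assumed equal in the fed and fasted conditions. The one weakness of (ii) that it admits concerns inference: "the associated standard errors and confidence intervals (CI) are not appropriate for our within-subjects crossover study design". That is its reason for adding the mixed model in (iii).

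**The concern.** A replicated crossover allows a participant's stable response to be separated from visit-to-visit noise. Approach (ii) keeps the noise of a single visit in both SDs and relies on subtraction to cancel it. Cancellation holds only on average, and only if the noise is the same size in both conditions. A meal and a fast could plausibly differ in this respect.

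At stake is the point estimate that the SAP will report as the true variation in response and read beside its threshold for individual responses. More sampling error means more outcomes where a real individual response gives a negative difference and SD_IR has no real value. Unequal noise would shift the estimate itself.

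**Working it through.** **Inputs.** From the SAP: the formula, the pooling of replicate SDs, and two visits per condition. The SAP states no SD, reliability or sample size for this estimate, so there is no figure to reproduce. All values below are assumptions. The identity in step 1 also assumes that pooling is an equal-weight average of the two variances over the same participants; the cited pooling equation is not to hand.

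**Step 1: the identity.** For visits x1 and x2 with sample variances S1², S2² and covariance C:
- variance of the mean (x1+x2)/2 is (S1² + S2² + 2C)/4
- variance of the half-difference (x1−x2)/2 is (S1² + S2² − 2C)/4
- their sum is (S1² + S2²)/2, the pooled variance.

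So the planned SD_M² − SD_C² is the means-first difference plus (variance of meal half-differences − variance of control half-differences). A stable response cancels out of a half-difference.

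**Step 2: expectations.** Let control change = c + e_C and meal change = c + d + e_M, where d is the individual response and the e terms are independent visit noise.
- As planned: Var(d) + 2Cov(c,d) + (s²_eM − s²_eC)
- Means first: Var(d) + 2Cov(c,d) + (s²_eM − s²_eC)/2
- Covariance of the two replicate meal-minus-control effects: Var(d)

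Example with noise SD 1.5 (meal) and 1.0 (control): s²_eM − s²_eC = 2.25 − 1 = 1.25, and half of that is 0.625.

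| True Var(d) | Planned | Means first | Replicate covariance |
|---|---|---|---|
| 0 | 1.25 | 0.63 | 0.00 |
| 0.25 | 1.50 | 0.88 | 0.26 |

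Simulation at n = 30 (40,000 runs) gave these values. If the control visits were the noisier, the sign would reverse.

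**Step 3: precision under equal noise.** Let A be the stable between-person variance, T = Var(d) independent of c, and E the visit-noise variance, with normal errors. In units of 2/(n−1):
- Var(means first) = (A+T+E/2)² + (A+E/2)² − 2A²
- Var(planned) = the same + E²/2, from two half-difference variances contributing (E/2)² each.

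With E = 1:
- T = 0: means first = 2A + 0.5, so the excess is 0.5/(2A + 0.5)
- T = 0.5: means first = 3A + 1.25, so the excess is 0.5/(3A + 1.25)

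| Reliability A/(A+E) | A | Excess variance, T = 0 | Excess variance, T = 0.5E | Negative at n = 18, T = 0.5E: planned vs means first |
|---|---|---|---|---|
| 0.1 | 0.111 | 69% | 32% | 14.9% vs 11.1% |
| 0.3 | 0.429 | 37% | 20% | 20.0% vs 17.8% |
| 0.5 | 1.000 | 20% | 12% | 25.0% vs 23.7% |
| 0.7 | 2.333 | 10% | 6% | 31.1% vs 30.7% |

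The last column is simulated (40,000 trials per cell). The excess ratios do not depend on n.

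**Step 4: what pooling already gains.** Relative to one visit, pooling cuts the sampling variance of one condition's variance to (1+r²)/2, where r is the between-visit correlation: 0.50 at r = 0, 0.625 at r = 0.5 and 0.82 at r = 0.8. For SD_IR² at n = 30 with A = T = 0.25 and E = 1, the simulated sampling SD is 0.507 (single visit), 0.366 (pooled) and 0.316 (two-visit means). The mean is about 0.25 in all three.

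**The case against.** The strongest reply is that this is a choice between two legitimate estimators. Under equal noise both are unbiased for the same quantity, the planned one is stated and reproducible, and it uses every available visit. The replicates are also exploited elsewhere. Approach (i) provides that "The association between the first and second replicate of control-adjusted treatment effect will be quantified for each outcome using Pearson's correlation coefficients", and in (iii) "participant and participant-by-condition terms will be modelled as random effects". Separating response from visit noise therefore does not rest on (ii) alone. The gain is also modest at better reliability: at T = 0.5E the sampling SD is only 9%, 6% or 3% larger as planned at reliability 0.3, 0.5 or 0.7. With no individual response, where the 69% figure sits, the difference is negative about half the time either way.

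Most of this stands, and it sets the priority. It does not remove the point, because (i) and (iii) leave the SD_IR reported from (ii) unchanged.

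A reader might infer more than the SAP supports:
- That pooling inflates SD_IR. It does not do so in general: the noise enters both SDs and cancels in expectation when equal, and otherwise the bias can go either way.
- That the replication is wasted. It is not: step 4 shows a clear gain over a single visit.
- That averaging first cures the bias. It halves it.

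**Conclusion.** The point holds as a cheap improvement, not as an error in the SAP. With complete data, means-first has the same expectation as the planned estimate under equal visit noise. It has smaller sampling error at every reliability examined, and half the bias when noise differs.

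The gain is worth having at low reliability and is nearly nil at 0.7, where negative differences are about 31% either way. All sizes assume normal errors, equal noise (except in the bias example), response independent of the control change and, for the negative shares, n = 18. Whether noise really differs between conditions, and by how much, cannot be judged from the SAP. The effect on conclusions around the individual-response threshold was not computed.

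Apart from efficiency, describing SD_IR as the true variation needs two conditions that the SAP leaves unstated: equal visit noise in the two conditions, and response uncorrelated with the control change.

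**What to change.** Replace the pooling parenthesis in approach (ii) with wording such as:

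> SD_M and SD_C are the SDs, across participants, of each participant's mean change over the two visits in that condition. SD_IR equals true response variation only if visit-to-visit variance is the same in both conditions and response is uncorrelated with the control change.

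Optional additions:
- Report the covariance of the two replicate meal-minus-control effects as a sensitivity estimate. It needs neither condition, and approach (i) already forms the same pairs. Its precision can be worse or better than planned: at n = 30 and true Var(d) = 0.25, the sampling SD was 0.418 against 0.366 with stable SD 0.5 and noise SD 1, but 0.146 against 0.286 with stable SD 1 and noise SD 0.5.
- Give SD_M² − SD_C² a 95% CI by resampling participants with all four visits kept together, which respects the crossover. This partly overlaps with the role of (iii).

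Cost: a sentence or two of SAP text and no new data. The downside is that a participant missing one replicate has a noisier mean and must be down-weighted or left out of this estimate, so the SAP should say which.

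### The genotype-by-condition effect and the participant-by-condition random effect never share a model, so within-genotype response variance is not estimated and the FTO interaction may get too small a standard error

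*SAP*

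**What the plan says.** The SAP title gives the study two linked aims: to "explore individual variability of appetite responses to a standardised meal and any moderating influence of the FTO gene".

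Individual variability is handled by three approaches. Approach (i) is one replicate correlation per outcome. Approach (ii) is an equation used "to provide an overall estimate of the true (control condition adjusted) between-subject differences in treatment response"; the SAP then says that "the associated standard errors and confidence intervals (CI) are not appropriate for our within-subjects crossover study design". For that reason it adds approach (iii), in which "a within-participant linear mixed model will be formulated to quantify any participant-by-condition interaction for each outcome". The fixed effects of (iii) are "Condition and period (sequence), and their interaction effects", and "participant and participant-by-condition terms will be modelled as random effects". None of the three approaches is described by genotype, and (iii) has no genotype term.

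Genotype appears in two other places. The first is the comparison of participant characteristics: "Between-genotype differences in participant characteristics will be quantified using linear mixed models with group (AA versus TT) modelled as a fixed factor". The second is the SPSS model for grand mean differences, which takes FTO genotype as a fixed between-subjects effect and quantifies its interaction with condition. That model is run "without the participant-by-condition random effect, but with a covariate of baseline values".

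**The concern.** The two quantities named in the title are kept in separate models, with two consequences.

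First, (iii) gives total response variance over AA and TT participants together. No planned output gives the variance left once genotype is accounted for. The SAP sets a minimal important difference for individual responses (0.1 baseline SDs). If the response SD exceeds it, a reader cannot tell from the planned outputs how far that reflects FTO and how far it reflects differences among people of the same genotype.

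Second, genotype-by-condition compares participants' meal effects between groups, so its standard error should include the variation of true meal effects among participants. The SPSS model leaves out the term that carries this variation, which is the term (iii) exists to detect. If individual response is real, the plan's one FTO moderation test may be anti-conservative, with a CI that is too narrow.

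**Working it through.** The SAP states no sample size, power or variance figure, so there is no planned figure to reproduce. The check is a comparison of model terms, followed by an illustration on assumed values.

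**1. Model terms, from the SAP**

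| Term | Approach (iii) | SPSS mean model |
|---|---|---|
| Condition | fixed | fixed |
| Period (sequence), and its interaction with condition | fixed | not stated |
| Participant-by-condition | random | omitted |
| Genotype, genotype-by-condition | absent | fixed |
| Baseline value | not stated | covariate |

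The participant-by-condition effect and genotype-by-condition are never fitted together.

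**2. Total and within-genotype variance**

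Assume equal AA and TT groups whose mean meal effects differ by D within-genotype response SDs. With within-genotype variance 1, total variance is 1 + D²/4, and the genotype share is (D²/4)/(1 + D²/4).

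| D | D²/4 | Genotype share |
|---|---|---|
| 0.2 | 0.01 | 1% |
| 0.5 | 0.0625 | 6% |
| 0.8 | 0.16 | 14% |
| 1.0 | 0.25 | 20% |
| 1.5 | 0.5625 | 36% |

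In simulation (20,000 runs per setting, N = 18 and 30, within-genotype variance 1.00), the variance estimated without genotype averaged about 1.16 at D = 0.8 and 1.59 at D = 1.5. With genotype-by-condition added it averaged about 1.00 in both cases. The documents do not fix D, so the gap between the two variances may be negligible or large.

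**3. Standard error of genotype-by-condition**

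Inputs: two conditions, each replicated twice (SAP). Assumed: equal groups, N participants in total, residual variance σ², a random participant intercept with independent residuals, no period effects, no baseline covariate, two-sided 5% level. Let τ² = kσ² be the variance among same-genotype participants in the true meal-minus-control effect. (If (iii) has one participant-by-condition variance common to both conditions, τ² is twice that component.)

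- Each participant's mean meal-minus-control difference has variance τ² + σ²(1/2 + 1/2) = σ²(1 + k). This is the correct error for the interaction.
- Without the random effect, the error is pooled from N − 2 degrees of freedom with mean square σ²(1 + k) and 2N degrees of freedom with mean square σ². Its expectation is σ²[1 + k(N − 2)/(3N − 2)], or about σ²(1 + k/3).
- The ratio of true to assumed variance is therefore about (1 + k)/(1 + k/3). The approximate error rate is the two-sided normal tail beyond 1.96/√ratio.

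| k | Ratio | √ratio | Approximate error rate | Simulated, N 12 to 40 |
|---|---|---|---|---|
| 0 | 1.00 | 1.00 | 5% | 0.049–0.051 |
| 0.5 | 1.5/1.167 = 1.29 | 1.13 | 8% | 0.083–0.086 |
| 1 | 2/1.333 = 1.50 | 1.22 | 11% | 0.108–0.117 |
| 2 | 3/1.667 = 1.80 | 1.34 | 14% | 0.146–0.154 |
| 4 | 5/2.333 = 2.14 | 1.46 | 18% | 0.182–0.192 |

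With the random effect included, the simulated error rate was 0.048–0.054 throughout. The simulated rates round to about 8%, 11%, 15% and 19%.

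**The case against.** The strongest reply is that the plan already answers the moderation question. Moderation by a group factor ordinarily means its interaction with condition, and the SAP quantifies that. The title promises no variance-explained figure, and the objectives may be set out in a protocol that is not shown. This stands: the omission of within-genotype variance is a gap against the title's aim, not a contradiction.

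A reader might infer that the plan cannot say whether genotype explains any of the variability. The SAP does not support that. A clear mean interaction implies that some is explained, and with equal groups D²/4 could be derived from it. What is missing is any planned estimate of the variance remaining within genotype.

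A reader might also infer that the variance from (iii) is inflated by genotype. It is not. Genotype differences are real differences between individuals, the three approaches are aimed at interindividual differences overall, and total variability is a legitimate target.

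The size of the gap is hypothetical: at D = 0.2 genotype accounts for 1% of response variance. A percentage reduction between two fits would also be a fragile summary. With balanced data and moment estimates it is negative whenever the genotype-by-condition F is below 1. For assumed N of 20 to 40, equal groups and residual variance 0.5 to 2 times response variance, the probability of that is about 67% at D = 0, 62–65% at D = 0.2 and 37–58% at D = 0.5. It is undefined if the first variance estimate is zero. Both points stand, and the fix avoids the percentage. Dropping the planned baseline covariate would also need a reason, and none is apparent, so the fix keeps it.

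None of this answers the standard-error point.

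**Conclusion.** The concern holds in a limited form and the SAP should be changed. As written, it estimates mean FTO moderation and total individual response variance, but not the response variance within genotype.

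The interaction standard error is a conditional problem. Given real individual response variance and a random participant intercept with independent residuals, a nominal 5% test runs at about 8% to 19% over response variances of 0.5 to 4 times residual. With no individual response variance it runs at about 5%.

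A reader might conclude that the planned FTO test is simply invalid. The documents do not go that far: the SPSS model's covariance structure is not stated, a richer structure could absorb some of the omitted variation, and the true response variance is unknown. The illustration leaves out the baseline covariate and period effects, so its figures show the order of magnitude only.

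**What to change.** 1. Keep (iii) as stated and label its participant-by-condition variance as total individual response.
2. For each outcome add a second fit with the same outcome, period terms and random effects, plus fixed genotype and genotype-by-condition. Label its participant-by-condition variance as within-genotype individual response.
3. Report that variance with its 95% CI from both fits. Do not rest conclusions on a percentage reduction.
4. Take the genotype-by-condition estimate and CI from a model that includes the participant-by-condition random effect and keeps the planned baseline covariate. The simplest way is to add that random effect to the planned genotype model. State that model's covariance structure in the SAP.

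Cost: a few lines of SAP text, one extra model per outcome, two fixed-effect degrees of freedom in the second fit, and no new data. The genotype-by-condition CI becomes somewhat wider. Under the assumptions above its standard error grows by about 13%, 22%, 34% and 46% at response variance 0.5, 1, 2 and 4 times residual (√ratio in the table), and hardly at all if there is no individual response.
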